7.2. Screening and Critical Baseline Assessments

Cardiovascular medical history, family history, and risk factors (as detailed in the eCRF) will be assessed at screening.

The following demographic parameters will be captured: year of birth, sex, race, and ethnicity.

Medical and medication history will be assessed as related to the inclusion/exclusion criteria listed in Section 5.

Procedures conducted as part of the subject's routine clinical management (e.g., blood count) and obtained before signing of informed consent may be utilized for screening or baseline purposes provided the procedure meets the protocol-defined criteria and has been performed in the time frame of the study.

7.3. Safety

Planned time points for all safety assessments are listed in the Time and Events Tables (Section 7.1). Additional time points for safety tests such as vital signs, physical examinations, and laboratory safety tests may be added during the course of the study based on newly available data to ensure appropriate safety monitoring.

7.3.1. Adverse Events and Serious Adverse Events

The definitions of an AE and an SAE can be found in [Appendix 5](#).

The investigator and their designees are responsible for detecting, documenting, and reporting events that meet the definition of an AE or SAE.

7.3.1.1. Time Period and Frequency for Collecting AE and SAE Information

- Any SAEs assessed as related to study participation (e.g., protocol-mandated procedures, invasive tests, or change in existing therapy) or related to a GSK product will be recorded from the time a subject consents to participate in the study up to and including any follow-up contact.
- Serious AEs will be collected from the signing of informed consent and AEs will be collected from the start of treatment until the follow-up contact (see Section 7.3.1.3) as indicated in the Time and Events Tables (Section 7.1).
- Medical occurrences that begin before the start of study treatment but after obtaining informed consent may be recorded on the Medical History/Current Medical Conditions section of the eCRF.
- All SAEs will be recorded and reported to GSK within 24 hours, as indicated in [Appendix 5](#).
- Investigators are not obligated to actively seek AEs or SAEs in former study subjects. However, if the investigator learns of any SAE, including a death, at any time after a subject has been discharged from the study, and he/she considers the

event reasonably related to the study treatment or study participation, the investigator must promptly notify GSK.

NOTE: The method of recording, evaluating, and assessing causality of AEs and SAEs plus procedures for completing and transmitting SAE reports to GSK are provided in [Appendix 5](#) and [Appendix 6](#).

7.3.1.2. Method of Detecting AEs and SAEs

Care will be taken not to introduce bias when detecting AEs and/or SAEs. Open-ended and non-leading verbal questioning of the subject is the preferred method to inquire about AE occurrence. Appropriate questions include:

- “How are you feeling?”
- “Have you had any (other) medical problems since your last visit/contact?”
- “Have you taken any new medicines, other than those provided in this study, since your last visit/contact?”

7.3.1.3. Follow-up of AEs and SAEs

After the initial AE/SAE report, the investigator is required to proactively follow each subject at subsequent visits/contacts. All SAEs, and non-serious AEs of special interest (as defined in Section 4.6.1) will be followed until resolution, until the condition stabilizes, until the event is otherwise explained, or until the subject is lost to follow-up (as defined in Section 5.4). Further information on follow-up procedures is given in [Appendix 5](#).

7.3.1.4. Regulatory Reporting Requirements for SAEs

Prompt notification by the investigator to GSK or designee of SAEs related to study treatment (even for non-interventional post-marketing studies) is essential so that legal obligations and ethical responsibilities towards the safety of subjects and the safety of a product under clinical investigation are met.

GSK has a legal responsibility to notify both the local regulatory authority and other regulatory agencies about the safety of a product under clinical investigation. GSK will comply with country specific regulatory requirements relating to safety reporting to the regulatory authority, IRB/ IEC and investigators.

Investigator safety reports are prepared for suspected unexpected serious adverse reactions according to local regulatory requirements and GSK policy and are forwarded to investigators as necessary.

An investigator who receives an investigator safety report describing an SAE(s) or other specific safety information (e.g., summary or listing of SAEs) from GSK will file it with the IB and will notify the IRB/IEC, if appropriate according to local requirements.

7.3.2. Pregnancy

Details of all pregnancies in female subjects and female partners of male subjects will be collected after the start of dosing and until the Follow-up visit (7 to 10 days post-last dose).

If a pregnancy is reported then the investigator should inform GSK within 2 weeks of learning of the pregnancy and should follow the procedures outlined in [Appendix 8](#).

7.3.3. Physical Examinations

A complete physical examination will include, at a minimum, assessments of the head, eyes, ears, nose, throat, skin, thyroid, neurological, lungs, cardiovascular system, gastrointestinal system, abdomen (liver and spleen), lymph nodes, and extremities. Height and weight will also be measured and recorded.

A brief physical examination will include, at a minimum, assessments of the skin, lungs, cardiovascular system, gastrointestinal system, and abdomen (liver and spleen).

7.3.4. Vital Signs

Vital signs should be taken with the subject in a semi-supine position, having rested in this position for at least 5 minutes and will include temperature, systolic and diastolic BP, pulse rate, and respiratory rate. Refer to Section [5.4.5](#) for vital sign stopping criteria.

7.3.5. Electrocardiograms

Triplicate 12-lead ECGs will be obtained at least 5 minutes apart for the time points that are within 1 hour before dosing. Single 12-lead ECGs will be obtained at all other time points during the study. All 12-lead ECGs will be obtained using an ECG machine that automatically calculates the heart rate and measures PR, QRS, QT, and QTc intervals. Refer to Section [5.4.4](#) for QTc stopping criteria.

7.3.6. Continuous Cardiac Monitoring

Continuous dual-lead telemetry will be initiated on Day -1 at least 8 hours before study drug administration on Day 1 and will continue until 48 hours post dose.

7.3.7. Clinical Safety Laboratory Assessments

All protocol required safety laboratory assessments, as defined in [Table 7](#), must be conducted in accordance with the Laboratory Manual, and Protocol Time and Events Tables (Section [7.1](#)). Laboratory requisition forms must be completed and samples must be clearly labelled with the subject number, protocol number, site/center number, and visit date. Details for the preparation and shipment of samples will be provided by the laboratory and are detailed in the Study Reference Manual (SRM). Reference ranges for all safety parameters will be provided to the site by the laboratory responsible for the assessments.

If additional non-protocol specified laboratory assessments are performed at the institution's local laboratory and result in a change in subject management or are considered clinically significant by the investigator (e.g., SAE or AE or dose modification) the results must be recorded in the eCRF.

Refer to the SRM for appropriate processing and handling of samples to avoid duplicate and/or additional blood draws.

Hematology, clinical chemistry, urinalysis, and additional parameters to be tested are listed in [Table 7](#).

Table 7 Protocol Required Safety Laboratory Assessments

Laboratory Assessments	Parameters			
Hematology	Platelet Count	Total iron ¹	RBC Indices:	WBC count with Differential:
	RBC Count	TIBC ¹	MCV	Neutrophils
	Hemoglobin	Ferritin ¹	MCH	Lymphocytes
	Hematocrit		MCHC	Monocytes
	Reticulocytes ¹			Eosinophils
				Basophils
Additional Iron Tests ²	Transferrin (apotransferrin)		Ceruloplasmin	Haptoglobin/Hemopexin
Clinical Chemistry ³	Blood urea nitrogen	Potassium	AST	Total and direct bilirubin
	Creatinine	Sodium	ALT	Total protein
	Glucose	Calcium	Alkaline phosphatase	Albumin
	Bicarbonate	Chloride	Uric acid	
Urinalysis	
 • Specific gravity • pH, glucose, protein, blood and ketones by dipstick • ACR⁴ • Microscopic examination (if blood or protein is abnormal) • NGAL⁵ • KIM-1⁵ • Urine color⁶ 			
Other Screening Tests	
 • Human immunodeficiency virus • Hepatitis B surface antigen • Hepatitis C antibody • Follicle-stimulating hormone and estradiol (as appropriate) • Alcohol, cotinine, and drug screen (to include at minimum: amphetamines, barbiturates, cocaine, opiates, cannabinoids and benzodiazepines) • β-human chorionic gonadotropin pregnancy test (if female of child-bearing age; serum at screening and urine at Day -1 and follow-up) 			

ACR = albumin to creatinine ratio, ALT = alanine aminotransferase, AST = aspartate aminotransferase, KIM-1 = kidney injury molecule 1, MCH = mean corpuscular hemoglobin, MCHC = mean corpuscular hemoglobin concentration, MCV = mean corpuscular volume, NGAL = Neutrophil gelatinase-associated lipocalin, RBC = red blood cell, TIBC = total iron binding capacity, WBC = white blood cell
 
Footnotes are on the next page.
				

NOTES:

1. In Parts 1 and 3, analyzed on Day –1 and at Follow-up visit. In Part 2, analyzed on Day –1, Day 5, Day 15, and at Follow-up visit.
2. Blood samples will be collected on Day –1, predose (at least 1 hour before dosing) on Days 5, and 15, and at Follow-up visit..
3. Details of Liver Chemistry Stopping Criteria and Required Actions and Follow-Up Assessments after liver stopping or monitoring event are given in Section 5.4.1, Appendix 2, and Appendix 3.
4. The ACR on urine albumin and creatinine will be determined using the first morning void urine at Screening and Follow-up visit for all subjects in both parts of the study. In addition, the ACR will be determined on Day 2 in Parts 1 and 3, and Days 5 and 15 in Part 2. Screening ACR may be performed on urine during the screening visit. Subjects should be provided a sterile urine transport container and instructions on how to collect a first void urine at home for screening. In the event a subject fails by ACR, the subject should be contacted to bring back first void urine for recheck. For the Follow-up visit, subjects must be provided a sterile urine transport container on discharge from the clinical unit and instructed to bring back the first morning void urine on the day of their return Follow-up visit.
5. An aliquot of the remaining urine samples will be banked and may be analyzed for NGAL and KIM-1 after the end of the study if a clinical signal is detected. Instructions for collection and storage of these urine samples are included in the Study Reference Manual.
6. Assessed before dosing on Day 15 (Part 2) only.

All laboratory tests with values that are considered clinically significantly abnormal during participation in the study (from first dose of study treatment through the Follow-up visit) should be repeated until the values return to normal or baseline. If such values do not return to normal within a period judged reasonable by the investigator, the etiology should be identified and the sponsor notified.

7.4. Pharmacokinetics

7.4.1. Blood Sample Collection

Blood samples for PK analysis of GSK3342830 will be collected at the time points indicated in the Time and Events Tables (Section 7.1). The actual date and time of each blood sample collection will be recorded. The timing of PK samples may be altered and/or PK samples may be obtained at additional time points to ensure thorough PK monitoring.

At the end of the study, the saved blood samples from a predicted therapeutically-relevant dose level and higher dose level for plasma PK analysis of parent and the highest dose level completed for metabolite profile, will be transferred to a GSK specified laboratory.

A total of 3 mL of blood will be collected from each subject.

Details of PK blood sample processing, storage, and shipping procedures are provided in the SRM.

7.4.2. Urine Sample Collection

Urine samples for PK analysis of GSK3342830 will be collected at the time points indicated in the Time and Events Tables (Section 7.1). The actual date and time of each urine sample collection will be recorded. The timing of urine samples may be altered and/or samples may be obtained at additional time points to ensure thorough PK monitoring.

At the end of the study, saved urine samples from a predicted therapeutically-relevant dose level and higher dose level for urinary PK analysis of parent and the highest dose level completed for potential metabolite profile, will be transferred to a GSK specified laboratory.

Urine will be collected in opaque bottles to maintain the blind of blinded study site personnel.

Details of PK urine sample processing, storage, and shipping procedures are provided in the SRM.

7.4.3. Sample Analysis

Concentrations of GSK3342830 will be determined in blood and urine samples using the currently approved bioanalytical methodology. Raw data will be archived at the bioanalytical site (detailed in the SRM).

Once the plasma and urine have been analyzed for GSK3342830 any remaining blood and urine may be analyzed for other compound-related metabolites and the results reported under a separate protocol.

7.5. Genetics

Depending on the clinical study results, exploratory pharmacogenomics analyses may be performed to examine the potential relationship between genetic variants and clinical endpoints.

Information regarding genetic research is included in [Appendix 4](#).

8. DATA MANAGEMENT

- For this study subject data will be entered via an eCRF into Oracle Clinical Remote Data Capture System (OC RDC). Subject data will be available for viewing through access to the OC RDC system. Data provided from other sources will be received, reconciled, combined, and transferred to GSK at predetermined time points.
- Management of clinical data will be performed in accordance with applicable GSK standards and data cleaning procedures to ensure the integrity of the data, e.g., removing errors and inconsistencies in the data.
- Adverse events and concomitant medications terms will be coded using Medical Dictionary for Regulatory Activities (MedDRA) and an internal validated medication dictionary, GSKDrug.
- The eCRFs (including queries and audit trails) will be sent at the end of the study in electronic format to GSK to be retained, and copies will be sent to the investigator to maintain as the investigator copy. Subject initials will not be collected or transmitted to GSK according to GSK policy.

9. STATISTICAL CONSIDERATIONS AND DATA ANALYSES

All statistical analyses will be performed by PPD using SAS (SAS Institute Inc., Cary, North Carolina, USA), version 9.2 or higher. Pharmacokinetic parameters will be calculated using Phoenix WinNonlin (Certara, L.P., [name]), version 6.3 or higher.

Before database lock, a reporting and analysis plan (RAP) will be issued as a separate document, providing detailed methods for the analyses outlined below.

Any deviations from the planned analyses will be described in a RAP addendum and justified in the final integrated clinical study report.

9.1. Hypotheses

The primary objective of this study is to investigate the safety and tolerability of GSK3342830 after administration of single and repeat IV doses in healthy adult subjects and after administration of single IV dose in adult Japanese subjects. The pharmacokinetics of GSK3342830 after administration of single and repeat IV doses in healthy subjects (and in adult Japanese subjects after administration of single IV dose) will also be determined. No formal statistical hypotheses are to be tested. For dose proportionality, accumulation, time invariance, and assessment of steady-state, an estimation approach will be taken, and point estimates and confidence intervals (CIs) will be constructed. For safety parameters, comparisons to placebo will be made based on descriptive statistics.

9.2. Sample Size Considerations

9.2.1. Sample Size Assumptions

Sample size is based on feasibility. No formal calculation of power or sample size for Parts 1 or 2 of the study will be performed. A sample size of 6 to 10 subjects per dose level cohort should be sufficient to provide useful estimates of both inter- and intra-subject variability for GSK3342830 PK parameters, and initial safety assessment.

Although the sample size is not based on statistical criteria, general probabilities can be determined on the likelihood of observing AEs. With 6 subjects receiving each dose of active drug, if the true adverse outcome rate is 5%, the chance of observing at least 1 adverse outcome at a given dose is 26%. Similarly if the true adverse outcome rate is 20%, the chance of observing at least 1 adverse outcome at a given dose is 73%. This level of predictivity is deemed adequate within this FTIH setting before commencing to repeat dosing (Part 2) and Phase II studies.

9.2.2. Sample Size Sensitivity

Not applicable.

9.2.3. Sample Size Re-estimation or Adjustment

Not applicable.

9.3. Data Analysis Considerations

In general, descriptive summaries will include number of subjects, mean, standard deviation, median, minimum, and maximum for continuous variables; and percent for categorical variables. Summaries will present data by dose level and where appropriate, by assessment time.

9.3.1. Analysis Populations

The **Safety Population** will consist of all subjects who receive at least 1 dose of study drug and have at least one post-dose safety assessment.

The **PK Population** will consist of all subjects who receive at least 1 dose of GSK3342830 and for whom a PK sample is collected and analyzed.

The **PK Parameter Population** will consist of all subjects in the PK population for whom valid and evaluable PK parameters were derived.

9.3.2. Interim Analysis

No formal interim analysis is planned for this study. However, one may be conducted in the event of clinically significant safety or PK findings. All preliminary safety, tolerability, and available PK data will be reviewed internally at GSK and with the clinical study site before each dose escalation in Part 1, before initiation of Part 2, and before each dose escalation in Part 2. All preliminary safety and tolerability data from Part 1 will be reviewed internally at GSK and with the clinical study site before dose selection for and initiation of Part 3. Section 6.4 provides further detail on data access and the handling of treatment blinding.

The relationship between dose and plasma GSK3342830 exposure, and associated variability will be characterized by a power model once data are available from 3 dose levels. Prior to that, prediction of the human exposure at the next dose will be based on population PK modeling (if feasible) or on the assumption of dose–exposure proportionality (i.e., doubling the dose gives an approximate doubling of exposure). If prior PK results show less than proportional increase in exposure with increasing dose, the prediction will be based on the assumption that the fold exposure increase to fold dose increase ratio will be the same with the current dose escalation as it was with the previous one. If prior PK results show more than proportional increase in exposure with dose, subsequent dose escalations will not be higher than 3-fold. The power model will be updated as data become available throughout the study. During dose escalation, a Bayesian predictive probability that a dose level will have mean AUC (AUC[0-t] or AUC[0-24] for single dose and AUC[0-24] for repeat dose) and C_{max} values greater than 2875 h•µg/mL and 2270 µg/mL (mean exposures at the NOAEL dose in the rat and monkey), respectively, and Bayesian predictive probability that an individual will have AUC(0-24) and C_{max} values greater than 3460 h•µg/mL and 2590 µg/mL (maximum

exposures at the NOAEL dose in the rat for AUC and the monkey for C_{max}), respectively, may be calculated for the next dose level and used together with safety and tolerability data to aid the next dose selection.

The Bayesian predictive probability will be based on Whitehead's model [Whitehead, 2001]:

$$y_{ij} = \theta_1 + \theta_2 d_{ij} + s_i + \epsilon_{ij}$$

where y_{ij} is log-PK of i-th subject to j-th dose, d_{ij} is j-th log-dose administered to i-th subject, θ_1 and θ_2 are population intercept and slope, respectively, s_i is random effect of i-th subject and ϵ_{ij} is random error of i-th subject in j-th dose.

9.4. Key Elements of Analysis Plan

9.4.1. Primary Analyses

Safety Analyses

The following safety evaluations will be performed:

- Monitoring for AEs
- Routine clinical laboratory tests including chemistry, hematology, and urinalysis
- Vital signs
- Twelve-lead ECG readings
- Continuous cardiac monitoring (dual-lead telemetry)

Safety endpoints will include AEs, clinical laboratory test results (chemistry [including liver function parameters], hematology, and urinalysis), vital signs (BP, heart rate, respiratory rate, and body temperature), and 12-lead ECG readings.

All safety data will be presented in data listings. Subject demographics, medical history, and prior and concomitant medications will be summarized for each dose level using descriptive statistics. For continuous variables, these summaries will include number of subjects, mean, median, standard deviation, minimum, and maximum.

For categorical variables, the summaries will include frequencies and corresponding percentages. No inferential hypothesis testing will be performed on the safety variables.

Adverse events will be coded using the MedDRA classification system.

Treatment-emergent AEs will be defined as any AEs, regardless of relationship to study drug, that occur after the dose of study drug until the Follow-up visit. The treatment-emergent AEs will be summarized for each dose level at AE onset for the overall number of AEs and percentage of subjects who experience them. The total number of AEs will be summarized by dose level and overall. The AEs will be further summarized by severity and relationship to the study drug. If relationship information is missing, the AE will be considered treatment related. Listings for the subsets of SAEs

and treatment-related SAEs will be provided. The SAEs and number of AEs leading to discontinuation will be summarized. The incidence of AEs will also be summarized by system organ class and preferred term.

Clinical laboratory test results, vital signs, and 12-lead ECG results will be summarized by actual values and change from baseline. Clinical laboratory values that are outside of the reference ranges will be flagged and evaluated for clinical significance by the investigator. Any 12-lead ECG abnormalities will be summarized by each dose level. Physical examination findings and cardiac telemetry results will be listed.

Detailed descriptions of the analyses in this study will be presented in the RAP.

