5.4.7. Additional Safety Stopping Criteria

Individual subjects, dosed with GSK3342830 who have experienced the following should be considered for potential discontinuation in consultation with the GSK medical monitor:

- Any Grade 4 AE
- Grade 3 gastrointestinal AE (see [Appendix 6](#))
 - *If a subject has 3 or more unformed stools in a 24-hour time frame, see [Appendix 10](#) to determine if samples should be collected for *Clostridium difficile* testing.*
- Grade 3 renal or urinalysis finding (see [Appendix 6](#))
- Severe hypersensitivity
- Anaphylaxis (see [Appendix 7](#))
- Subjects with a systolic BP of <90 mm Hg or a change in systolic BP from baseline of 30 mm Hg with symptoms. Vital signs should be taken with the subject in a semi-supine position, having rested in this position for at least 5 minutes and findings are confirmed upon repeat measurements taken within 5 minutes with the subject in the same physical position.

Data will be reviewed by the investigator and sponsor for consideration of potential study stopping if:

- Two (2) or more subjects, within a dose level, receiving GSK3342830 experience a Grade 3 renal or urinary AE that is deemed possibly or probably related to study drug by the investigator.
- Two (2) or more subjects, within a dose level, receiving GSK3342830 experience Grade 3 hypersensitivity related AE that is deemed possibly or probably related to study drug by the investigator.
- Two (2) or more subjects, within a dose level, receiving GSK3342830 experience a Grade 3 AE of rash that is deemed possibly or probably related to study drug by the investigator.
- Two (2) or more subjects, within a dose level, receiving GSK3342830 experience a Grade 3 vital sign (heart rate or BP) abnormality that is considered an AE and is deemed possibly or probably related to study drug by the investigator. Vital signs should be taken with the subject in a semi-supine position, having rested in this position for at least 5 minutes and findings are confirmed upon repeat measurements taken within 5 minutes with the subject in the same physical position.
- One (1) or more subjects receiving GSK3342830 experience anaphylaxis that is deemed possibly or probably related to study drug by the investigator.

The grading for AEs is based on the US National Institute of Allergy and Infectious Diseases Division of Microbiology and Infectious Diseases (DMID) Adult Toxicity Table (see [Appendix 6](#)).

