## 1. REPORTING & ANALYSIS PLAN SYNOPSIS

Overview	Key Elements of the RAP
Purpose	
The purpose of this reporting and analysis plan (RAP) is to describe:
 
 
Any planned analyses and output to be included in the clinical study report for Protocol 204847.
 

Protocol	
 
This RAP is based on the original protocol (Dated: 18-FEB-2016) of study 204847 (GSK Document No. : 2015N257523_00).
 

Primary Objective	
 
For Part 1, to investigate the safety and tolerability of GSK3342830 after administration of single IV doses in healthy adult subjects
 
For Part 2, to investigate the safety and tolerability of GSK3342830 after administration of repeat IV doses in healthy adult subjects
 
For Part 3, to investigate the safety and tolerability of GSK3342830 after administration of a single IV dose in healthy adult Japanese subjects
 

Primary Endpoint	
 
Clinical safety data from adverse events (AEs), clinical laboratory tests, vital signs (blood pressure, heart rate, temperature, and respiration rate), and 12-lead electrocardiogram (ECG) readings
 

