## 2. SUMMARY OF KEY PROTOCOL INFORMATION

### 2.1. Changes to the Protocol Defined Statistical Analysis Plan

Not applicable.

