## 7. PRIMARY STATISTICAL ANALYSES

### 7.1. Safety Analyses

#### 7.1.1. Overview of Planned Safety Analyses

The safety analyses will be based on the Safety population, unless otherwise specified.

Table 3 provides an overview of the planned Safety analyses, with full details of data displays being presented in Appendix 11: List of Data Displays.

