## 10.11.5. Safety Tables

Safety : Tables					
No.	Population	IDSL / TST ID / Example Shell	Title	Programming Notes	Deliverable [Priority]
Adverse Events					
2.1	Safety	AE2	Relationship of Adverse Event System Organ Classes, Preferred Terms and Verbatim Text		SAC [1]
2.2	Safety	AE1	Summary of All Adverse Events		SAC [1]
2.3	Safety	AE1	Summary of Drug-Related Adverse Events		SAC [1]
2.4	Safety	A15	Summary of Common (>=5%) Non-serious Adverse Events by System Organ Class and Preferred Term (Number of Subjects and Occurrences)		SAC [1]
2.5	Safety	A16	Summary of Serious Adverse Events by System Organ Class and Preferred Term (Number of Subjects and Occurrences)		SAC [1]
Laboratory Measurements					
2.6	Safety	LB1	Summary of Clinical Chemistry Values		SAC [1]
2.7	Safety	LB1	Summary of Clinical Chemistry Change from Baseline		SAC [1]
2.8	Safety	LB1	Summary of Haematology Values		SAC [1]
2.9	Safety	LB1	Summary of Haematology Change from Baseline		SAC [1]
2.10	Safety	UR3b	Summary of Urinalysis Dipstick Results		SAC [1]
Electrocardiograms					
2.11	Safety	EG1	Summary of ECG Findings		SAC [1]
2.12	Safety	EG2	Summary of ECG Values		SAC [1]
2.13	Safety	EG2	Summary of Change from Baseline in ECG Values		SAC [1]
2.14	Safety	SAFE_T1	Summary of Frequency of Maximum Post-Dose ECG Parameter Corrected QTc Interval		SAC [1]

Safety : Tables					
No.	Population	IDSL / TST ID / Example Shell	Title	Programming Notes	Deliverable [Priority]
2.15	Safety	SAFE_T2	Summary of Frequency of Maximum Change from Baseline for ECG Parameter Corrected QTc Interval		SAC [1]
Vital Signs					
2.16	Safety	VS1	Summary of Vital Signs		SAC [1]
2.17	Safety	VS1	Summary of Vital Signs Change from Baseline		SAC [1]

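### The SAP's safety tables leave out two AE summaries that the protocol's primary analysis promises: AEs by severity, and the number of AEs leading to discontinuation

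*Protocol*

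**What the plan says.** Two consecutive commitments stand in Protocol 9.4.1, which describes the primary (safety) analysis. The first is "The AEs will be further summarized by severity and relationship to the study drug". The second is "The SAEs and number of AEs leading to discontinuation will be summarized". Between them the section asks separately for listings of SAEs and of treatment-related SAEs, so it distinguishes a summary from a listing. It leaves the detail to the analysis plan: "Detailed descriptions of the analyses in this study will be presented in the RAP".

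The SAP presents itself as the place where that detail is found. Its synopsis gives its purpose as describing "Any planned analyses and output to be included in the clinical study report for Protocol 204847". Section 7.1.1 gives an overview of the safety analyses in Table 3, "with full details of data displays being presented in Appendix 11: List of Data Displays". Section 10.11.1 numbers the safety tables 2.1 to 2.17, and Section 10.11.5 names each one. Under Section 2.1, which is reserved for changes to the protocol-defined analysis, the entry is "Not applicable".

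**The concern.** Safety and tolerability are the primary objective in all three parts. Protocol 9.1 says that safety comparisons with placebo rest on descriptive statistics, and 9.4.1 rules out inferential testing. The descriptive tables are therefore the primary result. If the protocol promises a summary and the SAP's display list does not contain it, a programmer working from that list will not produce it, and the study report will not show it.

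Without a severity summary, a reader sees how many subjects had each event at each dose and on placebo, but must go to by-subject listings to see whether the events were milder or more severe at higher doses. Without a count of AEs leading to discontinuation, a basic tolerability figure for the repeat-dose cohorts has to be assembled by hand. Because SAP 2.1 declares no change, nobody has been asked to justify either omission.

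**Working it through.** No calculation applies. The check is a reconciliation of the four elements in the two protocol sentences against SAP Table 3, the Appendix 11 display list and the mock shells.

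| Element in Protocol 9.4.1 | SAP Table 3 | Summary table in Appendix 11 | Other display |
|---|---|---|---|
| AEs by relationship | Table and listing | Table 2.3 | Listing 13 |
| AEs by severity | No entry | None | Intensity column in the shells of Listings 12 to 14 |
| SAEs | Listing only | Table 2.5 | Listing 14 |
| Number of AEs leading to discontinuation | Withdrawal AEs: listing only | None | Listing 15; Table 1.2 counts subjects, not AEs |

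1. **AE tables.** Tables 2.1 to 2.5 are the only ones on AEs. They give the mapping of verbatim text to coded terms, all AEs, the "Summary of Drug-Related Adverse Events", common non-serious AEs, and SAEs. Tables 2.6 to 2.17 cover laboratory values, ECGs and vital signs.

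2. **Shells.** A general title could hide severity rows, so the shells were read. Tables 2.2 and 2.3 have system organ class and preferred term in the rows and dose groups in the columns. Table 2.4 adds occurrences. Table 2.5 adds drug-related and fatal counts. None has a severity row or column.

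3. **Discontinuation.** Table 3 alone would not settle this, because it marks serious AEs as listing-only although Table 2.5 exists. For withdrawal AEs, however, Table 3 and Appendix 11 agree on a listing and no table.

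4. **Version.** The SAP synopsis names the original protocol as its basis, while its reference list cites Amendment 1. The amendment's list of changes goes from Section 9.3.2 to 9.4.2 and 9.4.3 and shows nothing for 9.4.1, so a difference in version does not explain the gap.

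5. **Count.** There are 17 safety tables, of which 5 are on AEs, 0 are by severity and 0 are on AEs leading to discontinuation. Of the 4 promised elements, 2 have a table and 2 do not.

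6. **Where it bites.** The planned active groups number 6 (Part 1) + 3 (Part 2) + 1 (Part 3) = 10. The severity gap affects all 10 and placebo. For discontinuation of dosing, 6 + 1 = 7 groups receive one infusion and have no later dose to stop, so that count is informative mainly in the 3 Part 2 cohorts.

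**The case against.** The best defence is that nothing is lost. Listing 12 gives the intensity of every AE by part and treatment, and its shell also carries a withdrawal flag and the action taken. Cohorts have about 6 or 8 active and 2 placebo subjects, so a reader could tally by hand. Table 1.2 tabulates, by dose and placebo, the subjects whose primary reason for withdrawal was an AE, and separately those who met protocol-defined stopping criteria. Protocol Section 9 provides a correction route through a RAP addendum and justification in the study report. All of this stands, and it makes the point modest. It does not deliver what 9.4.1 promises: a listing is not a summary, and Table 1.2 counts subjects leaving the study rather than AEs leading to discontinuation.

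Listing 15 is not a full substitute. It is confined to withdrawal from the study, whereas the protocol also stops study treatment with continued follow-up, for example after a liver event. Its layout is also unsettled. Appendix 11 assigns the by-event AE shell, but the programmer's note points to Listing 11, which shows numbers of subjects and subject identifiers by term.

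A reader might infer more than the documents support:

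- *That the listing grades AEs on a different scale from the protocol.* Protocol Appendix 6 labels DMID Grades 1 to 4 as mild, moderate, severe and life-threatening, and the listing rows are mock entries. There is no mismatch.
- *That withdrawals due to AEs are only listed.* Table 1.2 contains a subject-level count.
- *That the missing tables are needed for the protocol's study-level reviews*, for example when two or more subjects at a dose level "experience a Grade 3 renal or urinary AE" judged possibly or probably related. Those reviews take place during conduct. The AE tables are final-analysis deliverables, produced after database freeze, and could not inform them.

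**Conclusion.** The point holds as a contradiction between the two documents. The protocol states two summaries of the primary endpoint that the SAP does not plan, and the SAP declares no change. The size is two missing elements of four. Severity is missing for all 10 planned active groups and placebo; the discontinuation count matters mainly for the 3 Part 2 cohorts. The consequence is a gap in the planned report, not a loss of data or a bias, and escalation decisions do not depend on it.

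The conclusion rests on reading Appendix 11 as the complete list of planned displays. The SAP does not call that list closed, but the stated purpose, the fixed number range and the named tables support the reading.

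**What to change.** In SAP Appendix 11, with matching entries in SAP Table 3:

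- Add a summary of treatment-emergent AEs by maximum severity (DMID grade), by dose and placebo. The protocol does not require a full cross-tabulation by system organ class and preferred term. Severity rows in Table 2.2 would meet the commitment and avoid a largely empty table in groups of 6 to 8.
- Add a count of AEs leading to discontinuation, by dose and placebo, with discontinuation of study treatment and of study shown separately.
- State which shell Listing 15 follows.

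If the sponsor prefers not to produce either summary, replace the entry in SAP 2.1 with a statement of the omission and the reason for it.

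The cost is a few rows in an existing table and one short new one. Intensity is already graded for every AE, and the AE listing shell already carries withdrawal and action taken, so no new data are needed. The change can be made before database lock.
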